4.3 Concomitant Treatments, Procedures, and Nondrug Therapies

All concomitant medications (prescription or over-the counter) as well as procedures or nondrug therapies (e.g. continuous positive airway pressure, pulmonary rehabilitation) will be recorded at the initial screening visit and updated at each subsequent visit. Except for other experimental treatments or medications with putative disease modifying effects

in FRAILTY, subjects will continue all prior concomitant medications for comorbid diseases to ensure optimal general medical care.

4.4 Withdrawal Criteria

Subjects will be informed that they have the right to withdraw from the study at any time and for any reason without prejudice to future or continued medical care. Subjects must be withdrawn for the following reasons:

1. Subject request.
2. Subject is unable or unwilling to comply with the protocol.
3. Medical reasons, at the discretion of the investigator.

Reason for withdrawal will be recorded in the subject's case report form. In order to adequately monitor for safety and potential efficacy outcomes, subjects who are withdrawn for any reason after receiving the first infusion should be encouraged to return for all assessments through the end of the study period. All efforts should be made to continue to record safety data and lung function parameters for all withdrawn subjects. Subjects who withdraw for reasons unrelated to the study or study drug (e.g. withdrawal of consent or loss to follow-up) may be replaced if deemed necessary to meet study objectives. Replacement subjects will be assigned unique identification numbers.

5. MESENCHYMAL STEM CELL DONORS

The availability of allogeneic hMSCs (allo-hMSC) offers the potential for an "off the shelf" product for subjects. Significant data has been generated to demonstrate that the allogeneic hMSCs are immunoprivileged and can be infused without immune rejection despite disparate HLA phenotypes.

Screening of allogeneic donors will follow standard transplant practices and all allogeneic donors will meet allogeneic donor eligibility criteria as outlined in 21 CFR Part 1271.

Allogeneic donor testing will include anti-HIV-1/2, anti-HTLV I/II, anti-HCV, HIV-1 nucleic acid testing, HCV nucleic acid testing, HBsAg, anti-HBc(IgG and IgM), CMV, West Nile Virus nucleic acid, *T. cruzi* ELISA (Chagas), Zika Virus and RPR. Potential donors testing positive for any of these infectious diseases with the exception of CMV, will be ineligible. Bone marrow (BM) aspirates will be obtained from normal individuals and allo-hMSCs will be isolated and expanded.

5.1 Bone Marrow Aspiration for Generation of MSCs

A total of approximately 60mL to 120mL of BM will be obtained from each normal volunteer. BM will be aspirated from the posterior iliac crest into heparinized syringes. The mononuclear cell fraction will be isolated using a density gradient with Lymphocyte Separation Media (specific gravity 1.077). The low-density cells will be collected and

washed with Plasma-LyteA containing 1% HSA. The washed cells will be sampled and viable cell numbers determined. The MNCs will be prepared antibiotic free (ie. No penicillin or streptomycin). The BM mononuclear cells will be seeded into 175 cm² tissue culture flasks in alpha MEM containing 20% FBS. After 14 days of culture, first passage (P0) cells will be harvested by trypsin treatment and expanded to passage 1, 2, and 3. At passage 3, cells are harvested and cryopreserved.

5.2 Normal Donor Eligibility

Donors (male or female) between the ages of ≥ 18 to ≤ 45 (inclusive) will be screened as potential BM donors. Donors will be evaluated by history and physical examination. The history will include:

- History of malignancy
- Bleeding abnormalities
- Prior deep venous thrombosis
- Known cardiac or pulmonary conditions
- Prior blood transfusions
- Vaccinations
- Questions to identify persons at risks of infectious disease transmission, including Zika virus
- Questions to identify persons at risk of transmitting hematological or immunological disease
- A physician will administer the National Marrow Donor Program (NMDP) Questionnaire (a donor health history screening questionnaire).

The physical examination will include review of vital signs and evaluation for potential risks associated with the BM aspiration procedure. Prospective donors will have infectious disease testing including:

- Hepatitis B surface antigen (HBsAg)
- Anti-Hepatitis B core antibody (HBcAb)
- Anti-Hepatitis C virus antibody (HCV Ab)
- Anti-Human Immunodeficiency Virus (HIV) antibody (HIV 1/2)
- Cytomegalovirus antibody (CMV)
- HCV/HIV Nucleic Acid test
- West Nile Virus Nucleic Acid test
- Rapid Plasma Reagins (RPR)
- Human T-lymphotropic Virus I/II (HTLV I/II)
- *T. cruzi* ELISA test (Chagas disease)
- Zika Virus (RNA qualitative Real Time RT-PCR, Serum/Urine or Zika Virus Antibody (IgM), MAC-ELISA)
- V DRL (confirmation with FTA-ABS if needed (Syphilis))

Prospective donors will also have the following blood and urine tests:

- Complete blood count with differential

- Complete metabolic panel, magnesium, calcium, and uric acid
- Urinalysis
- Pregnancy test (Female only)

Eligibility Criteria for Normal Donors will include:

- Male and female gender
- No history of malignancy
- No active coagulopathy and/or hypocoagulable state
- No history of cardio/pulmonary conditions
- Negative tests for Hepatitis B, Hepatitis C, RPR, Chagas, HIV 1/2, HTLV I/II and NAT for HCV, HIV, Zika Virus, and WNV.
- Hemoglobin \geq 13.0 g/dL if male; and if female donor hemoglobin \geq 11.0 g/dL
- Platelet count 140,000 to 440,000/uL
- WBC 3.0 to 11.0 K/uL
- No anomalies on the CBC and differential suggestive of a hematopoietic disorder
- Creatinine \leq 1.5 mg/dL
- ALT \leq 112 IU/L
- Bilirubin $<$ 1.5 mg/dL
- No diabetes
- Systolic blood pressure \leq 170
- Diastolic blood pressure \leq 90
- No history of autoimmune disorders
- Negative serum or urine pregnancy test for female donors
- Body Mass Index (BMI) \leq 30

Female donors would need to be screened for pregnancy as the procedure may be an added risk to a fetus.

5.3 Donor Consent

Informed consent will be obtained from all potential donors. The procedure will be explained in terms the donor can understand, and will include information about the significant risks of the procedure. Potential donors will have an opportunity to ask questions, the right to refuse or withdraw consent, and access to the results of all tests.

Donors will need to have virology's redrawn if BMA procedure not completed 7 days from the initial virology results.

5.4 Follow-up Schedule for Donors

After discharge from the hospital, the bone marrow donor will be contacted by the study team with a follow-up telephone call to determine the well-being, health status of the donor and/or if any adverse events have occurred. Attempts should be made to follow-

up via phone within a week of the BMA procedure. The donor will be provided with contact telephone numbers in the consent form for any questions or comments.

5.5 Biomarker Assessment for Donors

A separate 7 mL blood sample for gene expression profiling will be obtained at the donation visit. All samples will be identified so that they can be linked to individual subjects. These samples may be stored indefinitely. Individual results will not be returned to the subject or the study physician. The samples will be linked to subjects, but there will be no recontact. Data presented in publications will not contain individual subjects' clinical characteristics or outcomes; only aggregate data from the entire study will be disclosed.

6. TREATMENT OF SUBJECTS

6.1 Study Investigational Product

The investigational product (IP) consists of hMSCs obtained from a healthy bone marrow donor. Screening of allogeneic donors will follow standard transplant practices and all allogeneic donors will meet allogeneic donor eligibility criteria as outlined in 21 CFR Part 1271. BM will be obtained from normal volunteers with approximately 60 ml to 120 ml aspirated from the posterior iliac crest. The BM will be aspirated into heparinized syringes. The MNC fraction will be isolated using a density gradient with Lymphocyte Separation Media (specific gravity 1.077). The low-density cells will be collected and washed with Plasma-LyteA containing 1% HSA. The MNCs will be prepared antibiotic free (ie. No penicillin or streptomycin). The washed cells will be samples and viable cell numbers determined. The BM MNC will be seeded into 175 cm² tissue culture flasks in alpha MEM containing 20% FBS. After approximately 14 days of culture, passage zero (P0) cells will be harvested by trypsin treatment and expanded P1, P2 and P3. Cells are harvested using the Trypsin treatment and each passage lasts approximately 7 to 10 days. At P3, cells are harvested and cryopreserved. This process may or may not contain penicillin and/or streptomycin. Any subject that test positive for a penicillin or streptomycin allergy will be provided with an antibiotic free MSC product.

6.2 Dosing

During the pilot phase of the study 15 subjects will receive a single infusion of hMSCs

Group 1 will consist of Five (5) subjects and will be treated with a single administration of allogeneic hMSCs: 2×10^7 (20 million) cells delivered via peripheral intravenous infusion.

Group 2 will consist of Five (5) subjects and will be treated with a single administration of allogeneic hMSCs: 1×10^8 (100 million) cells delivered via peripheral intravenous infusion.

Group 3 will consist of Five (5) subjects and will be treated with a single administration of allogeneic hMSCs: 2×10^8 (200 million) cells delivered via peripheral intravenous infusion.

After subjects complete their Month 12 follow-up phone call visit in the pilot phase, all 15 subjects will then have the option of receiving up to three (3) additional infusions of allogeneic hMSCs: 1×10^8 (100 million) cells delivered via peripheral intravenous infusion. The option will be provided if subjects in the pilot phase continue to meet all inclusion / exclusion criteria. See Addendum A and Addendum C for rationale and description for initial 15 subjects.

In the randomized phase of allo-hMSCs or matched placebo 30 subjects will be randomized in a 1:1:1 ratio to one of two Treatment Strategies or placebo following successful completion of the Pilot Phase.

Group A will consist of 10 subjects who will receive 100 million Allogeneic hMSCs delivered via peripheral intravenous infusion.

Group B will consist of 10 subjects who will receive 200 million Allogeneic hMSCs delivered via peripheral intravenous infusion.

Group C will consist of 10 subjects who will receive placebo via peripheral intravenous infusion.

The Allo-hMSCs will be derived from donors meeting criteria for allogeneic unrelated human bone marrow stem cell source manufactured by the University of Miami or from a commercial clinical grade bone marrow source.

6.3 Dosage Rationale

A safety profile for IV infusion of hMSCs was based on results from previous completed toxicology results¹⁷. The results from previous studies demonstrate that the product can be administered intravenously without toxic events at up to 65×10^6 hMSC/kg dose delivered in one bolus infusion or at 100×10^6 hMSC/kg cumulative dose delivered by 5 infusions (20×10^6 hMSC/kg per infusion).

The evidence supports the conclusion that it is feasible to dose subjects in this study based on a standard dose of hMSCs rather than per kilogram of body weight. The total cell number corresponds to a range of $1.3 - 4.4 \times 10^6$ hMSCs per kg per infusion for subjects with 45 to 150kg body weight, the weight range for this study.

Therefore, results from previous trials support the rationale on the safety and potential efficacy of the selected maximum dose of 200×10^6 allo hMSCs.

6.4 Administration Rate

Prior clinical trials have used rates up to 30×10^6 hMSC/min where no infusion related toxicity was observed.

In the proposed study, the cell dose to be delivered is 20×10^6 , and 100×10^6 hMSC/infusion, and 200×10^6 reconstituted with the 2.5 million hMSC/ml, in the following total volume

- 25 ml for 20 million dose (5 million hMSC/min)
- 40ml for 100 million dose (5 million hMSC/min)
- 80ml for 200 million dose (5 million hMSC/min)

For the randomized double blinded phase we will prepare the following doses of 100 million, 200 million and Placebo in an 80ml bag.

Cell will be delivered at a rate of 2ml/min, and delivered at a maximum rate of 16×10^6 hMSC/minute and will last approximately:

- 12.5 minutes for 25ml for 20 million dose
- 40 minutes for 40ml for 100 million dose
- 40 minutes for 80ml for 200 million dose.

The infusion bag will be flushed with an additional 25 ml of 0.9% normal saline at the completion of allo-hMSC infusion and delivered at a rate of 2ml/min.

During the randomized phase each dose will take place over approximately 40 minutes in order to maintain the blind.

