This addendum protocol is designed to test the safety of sequential infusions of allogeneic mesenchymal stem cells 6 to 18 months following previous infusion. Subjects in this protocol have previously participated in protocols receiving open label infusions (phase I subjects). There is an important need to assess the safety and immunologic tolerability of additional doses of intravenous allogeneic MSCs in the target population. Previously a group of 12 subjects received two doses delivered 12-18 month apart with excellent safety and no adverse effects attributed to the study agent. A second group of 20 subjects received a single dose of MSCs, in the penicillin/streptomycin free cohort. Subjects receiving either one or two sequential doses have not mounted significant immunologic reactions to the study agent.

Subjects in the pilot phase would have received two (2) of the possible four (4) infusions of allogeneic MSCs and are eligible to participate in this optional follow-on phase. Additionally, subjects receiving one dose (100 Million cells) in the penicillin/streptomycin free protocol are eligible to receive up to three (3) additional infusions. Because several studies, reviewed below, have now shown safety of repeat doses of MSCs in a variety of medical conditions, additional safety testing in the subject population of aging frailty enrolled in the CRATUS trial is required⁹². All study specific processes and procedures included in the pilot phase and penicillin free follow-on phase of the protocol apply in this addendum unless otherwise noted.

Pilot subjects participating in this addendum are eligible to receive up to two (2) additional infusions and subjects participating from Penicillin Free cohort are eligible to receive up to three additional infusions of MSCs (100 Million cells) administered 6 -18 months apart. The MSCs provided to study subjects in this addendum may be penicillin/streptomycin free. Subjects from the Pilot phase returning for their additional infusions may receive cells with penicillin/streptomycin. Altogether, subjects will have received four (4) infusions over a time span ranging approximately 3 to 6 years. Subjects will have ongoing safety monitoring that will include detailed immunologic assessments.

Subjects that do not want an additional infusion will not be eligible to continue in the study and/or receive additional infusions under this addendum.

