Koc et al⁹⁴; further investigated Hurler syndrome (mucopolysaccharidosis type-IH) and metachromatic leukodystrophy (MLD) and studied allogeneic MSCs based on their potential to differentiate into cells of bone, cartilage, tendon, muscle and other adventitial tissues and offer potential for corrective cellular therapy⁹⁵. Their results demonstrated no infusion-related toxicity, improvement in nerve conduction, and bone mineral density was either maintained or improved in all subjects.

A Phase II study on the 3-year efficacy of allogeneic MSCs in the treatment of system lupus erythematosus (SLE) was reported by Lingyun Sun's group⁹⁶. The results of this study demonstrated the therapeutic efficacy of allogeneic MSCs in treating SLE. However, no advantage was found by administering a second or higher dose of allogeneic MSCs. Despite this lack of additional efficacy over a single dose, the results of this study confirmed the safety of multiple infusions of allogeneic MSCs. The doses (1×10^6 MSCs/kg body mass) were administered 1 week apart. Another study reported on the use of repeated dosing of allogeneic MSCs in subjects with chronic obstructive pulmonary disease. The study showed minimal therapeutic efficacy after 2 years¹⁹. Importantly, in this subject population repeated allogeneic MSC infusions, which were given 4 times at 30 day intervals (1×10^8 MSCs/infusion) were safe.

In the pilot phase of this trial, subjects (N=12) have been administered two doses of MSCs 12 to 18 months apart with no adverse effects.

Taken together, these various clinical studies provide a solid rationale for repeat allogeneic MSC infusions. In no case did the administration of multiple doses lead to a significant increase in the frequency of adverse effects, or to a decrease in therapeutic efficacy over a single dose. In many cases, repeated infusions indeed improved clinical outcomes, demonstrating an additive effect of allogeneic MSC therapy. Given these promising results, investigations are now warranted to determine optimal dosing frequency and total doses of allogeneic MSCs to administer.

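### Section 6.4's volume, concentration and cell rate for the 20 million pilot dose multiply out to 62.5 million cells, 3.1 times the dose

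*Combined protocol and SAP*

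**What the plan says.** The Synopsis and Section 6.2 give Group 1, five open-label pilot subjects, a single infusion of 20 million cells. Groups 2 and 3 receive 100 and 200 million.

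Section 6.4 introduces all three doses together as "reconstituted with the 2.5 million hMSC/ml, in the following total volume". The entry for Group 1 is "25 ml for 20 million dose (5 million hMSC/min" and the entry for Group 2 is "40ml for 100 million dose (5 million hMSC/min". Group 3 has 80 ml at the same cell rate. The section sets the flow at 2 ml/min, which Appendix 1 repeats, and lists durations of "12.5 minutes for 25ml for 20 million dose", "40 minutes for 40ml for 100 million dose" and 40 minutes for the 80 ml, 200 million dose. It also gives a maximum of 16 million cells/min and a 25 ml saline flush after the cells.

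Addendum C (C.2) reports that in the pilot phase "subjects (N=12) have been administered two doses of MSCs 12 to 18 months apart", so pilot dosing had already taken place when this version was written.

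**The concern.** Dose, volume, concentration, flow and duration are tied together by simple products, and for Group 1 they cannot all be true. Section 6.4 is where the protocol says how the lowest dose is made up and run, so the error sits in operative text.

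Three things could follow:

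- **Misreported rate.** If 20 million cells went into 25 ml, a report citing Section 6.4 would credit Group 1 with tolerating 5 million cells/min when it received 1.6 million/min. As printed, all three groups appear to get cells at the same rate, although Section 3.1 presents the pilot as a test of escalating dose and volume.
- **Misconverted exposure.** Appendix 1 has staff record the total volume infused. Converting that volume to cells at 2.5 million/ml would overstate Group 1 exposure 3.1-fold, including for a partial infusion.
- **Wrong dose.** More than 20 million cells would have been given only if the laboratory filled the bag by volume and concentration and not by cell count. Nothing in the documents shows that it did.

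The pilot safety data go to the DSMB before the randomized phase (Sections 9.3 and 9.4.3.3), so the lowest dose should be described correctly.

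**Working it through.** **Inputs.** Doses of 20, 100 and 200 million (Synopsis, Sections 6.2 and 6.4). Concentration 2.5 million/ml, volumes 25, 40 and 80 ml, cell rate 5 million/min, flow 2 ml/min, durations 12.5, 40 and 40 min (all Section 6.4).

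**Formulas.** Cells = volume × concentration. Cells = cell rate × duration. Duration = volume ÷ flow. Cell rate = concentration × flow.

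**Step 1: does the stated concentration reproduce the stated doses?**

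| Group | Volume × concentration | Stated dose | Ratio |
|---|---|---|---|
| 1 | 25 × 2.5 = 62.5 million | 20 million | 3.125 |
| 2 | 40 × 2.5 = 100 million | 100 million | 1 |
| 3 | 80 × 2.5 = 200 million | 200 million | 1 |

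Groups 2 and 3 reproduce exactly, so the formula is the intended one. Only Group 1 fails.

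**Step 2: second route for Group 1.** 25 ml ÷ 2 ml/min = 12.5 min, as stated, so volume, flow and duration agree with each other. But 5 million/min × 12.5 min = 62.5 million. This is not a second error: 2.5 million/ml × 2 ml/min = 5 million/min, so the printed rate carries the same concentration.

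**Step 3: the two self-consistent versions for 20 million cells.**

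- Keep 25 ml and 12.5 min: 20 ÷ 25 = 0.8 million/ml, and 0.8 × 2 = 1.6 million/min. Each is 32% of the stated figure (0.8 ÷ 2.5 = 1.6 ÷ 5 = 0.32).
- Keep 2.5 million/ml and 5 million/min: 20 ÷ 2.5 = 8 ml, and 8 ÷ 2 = 4 min.

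**Step 4: cell-rate step to Group 2, taking Group 1 as 1.6 million/min.** Section 6.4 is itself unclear here, because 40 ml at 2 ml/min takes 20 min, not the stated 40.

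- At 40 min: 100 ÷ 40 = 2.5 million/min, and 2.5 ÷ 1.6 = 1.56, a 1.6-fold step.
- At 20 min: 100 ÷ 20 = 5 million/min, and 5 ÷ 1.6 = 3.125, a 3.1-fold step.

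**Step 5: was Group 1 already dosed?** Twelve pilot subjects had two infusions. With 15 pilot subjects as planned, 10 of them outside Group 1, at least 12 − 10 = 2 came from Group 1.

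**The case against.** The strongest reply is that the 62.5 million figure depends on reading 2.5 million/ml as the final bag concentration. The sentence could instead mean that cells are reconstituted at 2.5 million/ml, which takes 8 ml for 20 million, and then brought up to a total of 25 ml. Dose, volume, flow and duration then agree, and only the bracketed rate is wrong. The 40 minutes given for the 100 million dose lends some support: at 2 ml/min that is 80 ml, or 100 ÷ 80 = 1.25 million/ml, so the section does not hold firmly to one delivered concentration.

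That reading may well describe what was done, but it does not rescue the line. The printed 5 million/min would still be wrong, since 1.6 follows. That rate divided by 2 ml/min also gives 2.5 million/ml as delivered, so the text itself points away from dilution. The flush is separate saline given after the cells, and 16 million/min is only a ceiling. Neither reconciles the figures.

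The objection is right that the consequence is small. The dose is 20 million wherever it is stated. Both candidate rates lie below the 16 million/min maximum and the 30 million/min cited from earlier trials. Even 62.5 million is below the Group 2 dose. Group 3 receives 200 ÷ 40 = 5 million/min, so the pilot tests that rate in any case. No endpoint or analysis uses cell rate. Sections 6.7.2 and Appendix 1 already require product and infusion records, so actual delivery should be recoverable.

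**Conclusion.** The point holds and is minor. At least one figure in the Group 1 line is wrong on every reading. Taken literally, the line gives 62.5 million cells against 20 million, a 3.1-fold mismatch. If 20 million cells were made up to 25 ml, which is the more likely case, the concentration and cell rate are overstated 3.1-fold.

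This rests on the 20 million dose being correct, as its consistent statement suggests, and on the 2 ml/min flow, which two sections give. The documents cannot show which preparation was used, and they do not show an overdose. The inference that at least two Group 1 subjects were dosed assumes the planned 15 pilot subjects in groups of five; Section 3.2 says approximately fifteen. The arithmetic does not depend on it.

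**What to change.** Keep the dose at 20 million. Correct the Group 1 entry in Section 6.4, most likely to 25 ml at 0.8 million/ml and 1.6 million/min over 12.5 min. If the batch records show 2.5 million/ml, the entry becomes 8 ml over 4 min at 5 million/min. Limit the 2.5 million/ml lead-in to the 100 and 200 million doses.

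Because pilot subjects have already been treated, a text edit alone is not enough. Check the five Group 1 batch records and report the cells, volume and rate actually delivered. Before quoting a rate step from Group 1 to Group 2, settle whether the 40 ml ran for 20 or 40 minutes.

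The cost is one corrected line and a check of five records. Visits, sample size and later phases do not change.
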